3.8.4. Weight, Body Mass Index, Waist Circumferences and Vital Signs

3.8.4.1. Weight, Body Mass Index, Waist Circumferences

Weight (kg), BMI (kg/m^2) and waist circumferences (baseline and change from baseline) for each visit will be summarized as overall for the open-label periods and by treatment group for the double-blind periods. Height (cm) will be measured at screening visit and this value will be used for the calculation of the BMI. All weight and BMI data will be listed.

Number and percentage of subjects with weight change values considered as PCS occurring at any post-baseline visit will be summarized by treatment group for the double-blind period. Criteria for PCS are presented below. The percentages will be calculated relative to the number of subjects in the safety population. A supportive listing will present all body weight for a subject and parameter for cases where at least one value was potentially significant.

Table 4: Criteria for Potentially Clinically Significant (PCS) Changes from Baseline in Body Weight

Parameter	Criteria
Body Weight	Decrease from Baseline $\geq 7\%$ Increase from Baseline $\geq 7\%$

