5.2.1. Clinical Studies

In the clinical studies of samidorphan to date, 469 subjects have received samidorphan orally (1-55.7 mg) or sublingually (1-16 mg) for up to 12 weeks. Commonly reported AEs observed across all studies included nausea, fatigue, and somnolence. Other AEs observed in these studies included dry mouth, vomiting, constipation, decreased appetite, headache, dizziness, and anorexia. Overall, no trends or clinically meaningful changes have been observed in clinical

laboratory analytes, vital sign parameters, or electrocardiogram (ECG) data. No deaths have occurred in these studies.

Samidorphan has been shown to block opioid agonist effects in opioid-experienced adults and decrease alcohol consumption in alcohol-dependent adults. In opioid-experienced adults, samidorphan blocked both the subjective (eg, Drug Liking measured with a visual analog scale [VAS]) and physiological effects (eg, pupil constriction measured with pupillometry) of the opioid agonists remifentanyl (Study ALK33-004) and buprenorphine (Study ALK33-008). In adults with alcohol dependence (N=410), samidorphan (1, 2.5, or 10 mg) was associated with a reduction in drinking behavior (Study ALK33-005) compared with placebo; the largest reduction was seen with the highest samidorphan dose administered in this study (10 mg).

In addition to the reduction of alcohol drinking, samidorphan may attenuate weight gain associated with olanzapine. A Phase 1 proof-of-concept study has been conducted in healthy adults (ALK33-301) to determine the safety, tolerability, and efficacy of samidorphan when taken with olanzapine to mitigate olanzapine-related weight gain. In this study, significantly less weight gain was seen in the ALKS 3831 treatment arm than in the olanzapine plus placebo arm. A Phase 2 study, ALK3831-302, is currently underway to evaluate (as a secondary outcome) attenuation of weight gain by ALKS 3831 compared with olanzapine plus placebo in subjects with schizophrenia.

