3.2.3. Safety Population

The safety population is defined as all randomized subjects who receive at least 1 dose of study drug (olanzapine, samidorphan or placebo) during the double-blind placebo-controlled treatment period.

Follow-up safety population is defined as subjects who entered into the follow-up period or have any newly emergent adverse events ([Section 3.8.1](#)).

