3.8.3. Clinical Laboratory Parameters

Laboratory parameters will be presented in conventional units. Only scheduled laboratory parameters will be included in the summaries. All laboratory data, including those collected at unscheduled visits, will be included in the listings.

Laboratory results (baseline and change from baseline) for chemistry and hematology parameters will be summarized as overall for open-label periods and by treatment group for the double-blind period.

Clinical laboratory test values, scheduled or unscheduled, will be considered potentially clinically significant (PCS) if they meet PCS criteria listed in Table 2. The number and percentage of subjects who have PCS post baseline clinical laboratory values will be tabulated by treatment group for the double-blind period. The percentages will be calculated relative to the number of subjects with available non-PCS baseline values and at least 1 post baseline assessment for the double-blind treatment period. The numerator will be the total number of subjects with available non-PCS baseline values and at least 1 PCS post baseline value for the double-blind treatment period. A supportive tabular display of subjects with PCS post baseline values will be provided, including the subject ID number, study center number, baseline, and all post baseline (including non-PCS) values.

Table 2: Criteria of Potentially Clinically Significant (PCS) Abnormality for Selected Analytes

Parameters	Criteria
Albumin	<2.5 g/dL
Alkaline phosphatase (U/L)	$\geq 3 \times \text{ULN}$
Alanine aminotransferase (U/L)	$\geq 3 \times \text{ULN}$
Aspartate aminotransferase (U/L)	$\geq 3 \times \text{ULN}$
Bilirubin, total	$\geq 2.0 \text{ mg/dL}$
Blood urea nitrogen	$> 30 \text{ mg/dL}$
Cholesterol, random	$> 300 \text{ mg/dL}$
Cholesterol, fasting	$\geq 240 \text{ mg/dL}$
Cholesterol, HDL fasting	$\leq 30 \text{ mg/dL}$
Cholesterol, LDL fasting	$\geq 160 \text{ mg/dL}$
Creatine kinase (U/L)	$\geq 3 \times \text{ULN}$
Creatinine	$\geq 2.0 \text{ mg/dL}$
Glucose, random	$< 50 \text{ mg/dL}$ or $\geq 200 \text{ mg/dL}$
Glucose, fasting	$\geq 126 \text{ mg/dL}$
Potassium	$< 3 \text{ mmol/L}$ or $> 5.5 \text{ mmol/L}$
Lactate dehydrogenase (U/L)	$> 3 \times \text{ULN}$
Phosphate	$< 2 \text{ mg/dl}$ or $> 5 \text{ mg/dl}$
Prolactin (female)	$> 30 \text{ ng/mL}$
Prolactin (male)	$> 20 \text{ ng/mL}$
Sodium	$< 130 \text{ mmol/L}$ or $> 150 \text{ mmol/L}$

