3.8.4.2. Vital Signs

Descriptive statistics for vital signs and changes from baseline values at each scheduled time point will be presented as overall for the open-label periods and by treatment group for the double-blind period.

Vital sign values will be considered PCS if they meet both the observed-value criteria and the change-from-baseline criteria listed in Table 5. The number and percentage of subjects with PCS post baseline values will be tabulated by treatment group for the double-blind period. The percentages will be calculated relative to the number of subjects with available baseline values and at least 1 post baseline assessment for the double-blind period. The numerator will be the total number of subjects with available baseline values and at least 1 PCS post baseline value for double-blind period. A supportive tabular display of subjects with PCS post baseline values will be provided, including the subject ID number, study center number, and baseline and all post baseline (including non-PCS) values.

All vital signs will be presented in the subject data listing.

Orthostatic hypotension (20/10) is defined as a fall in systolic blood pressure of at least 20 mmHg and a fall in the diastolic blood pressure of at least 10 mmHg upon standing from supine. Orthostatic hypotension (30) is defined as a fall in systolic blood pressure of at least 30 mmHg upon standing from supine.

Orthostatic tachycardia is defined as a heart rate increase of 30 beats per minute (bpm) or more upon standing from supine, or over 120 bpm upon standing.

The number and percentage of subjects with orthostatic hypotension or orthostatic tachycardia occurring at any post-baseline visit will also be summarized by treatment group for the double-blind period.

Table 5: Criteria for Potentially Clinically Significant (PCS) Blood Pressure or Pulse Rate

Parameter	Criteria
Supine Systolic Blood Pressure	≤ 90 and decrease ≥ 20 mm Hg ≥ 180 and increase ≥ 20 mm Hg
Supine Diastolic Blood Pressure	≤ 50 and decrease ≥ 15 mm Hg ≥ 105 and increase ≥ 15 mm Hg
Supine Heart Rate	≤ 50 and decrease ≥ 15 bpm ≥ 120 and increase ≥ 15 bpm

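### Body weight is the only potentially clinically significant (PCS) table whose percentages use the full safety population, so a dosed subject with no post-baseline weight counts as a non-event

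*SAP*

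**What the plan says.** SAP 3.8.4.1 counts subjects with "weight change values considered as PCS occurring at any post-baseline visit", by treatment group for the double-blind period. Its Table 4 sets the threshold at a 7% or greater increase or decrease from baseline. The section then fixes the denominator: "The percentages will be calculated relative to the number of subjects in the safety population".

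SAP 3.2.3 admits to the safety population any randomized subject with at least one dose of study drug in the double-blind period. It sets no condition on having a post-baseline measurement.

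The other PCS tables use a narrower denominator:

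- Laboratory (SAP 3.8.3): "number of subjects with available non-PCS baseline values and at least 1 post baseline assessment for the double-blind treatment period".
- Vital signs (SAP 3.8.4.2): "number of subjects with available baseline values and at least 1 post baseline assessment for the double-blind period".
- ECG (SAP 3.8.5): the same rule as for laboratory values.

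SAP section 7 adds two general rules. Summary tables rest on observed data without imputation unless stated otherwise, and unscheduled measurements count in the PCS analyses.

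**The concern.** The numerator can contain only subjects with a post-baseline weight, while the denominator contains everyone dosed. A subject never weighed after baseline is therefore handled as if a 7% change had been ruled out. The SAP does not call such a subject unchanged; the result follows from the division. It sits poorly with the observed-data rule in SAP section 7, and it departs without explanation from the convention in the section immediately following.

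Weight is a parameter that readers will want to compare between arms. Protocol 5.2.1 says that "samidorphan may attenuate weight gain associated with olanzapine" and reports less weight gain with the combination in a study of healthy adults. At stake is whether the two percentages describe subjects in whom a change could have been seen, and whether part of any gap between arms reflects who was weighed rather than who gained or lost weight.

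**Working it through.** The plan states no weight-change rate, so there is no figure of its own to reproduce. The check is algebraic.

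**Who is affected.** Protocol Table 2 schedules weight at Visit 8 (Study Week 3) and next at Visit 9 (Study Week 5), two weeks after randomization. Table 3 schedules it again at Visit 38/ET. Unscheduled weights also count (SAP section 7). A dosed subject lacks a post-baseline weight only by leaving before Visit 9 and having neither an ET weight nor an unscheduled one. This can happen: under Protocol 7.4, a subject who does not return for the ET visit is to be contacted by telephone, which yields no measured weight.

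**Inputs.**

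- N = 135 per arm, the planned randomized number (Protocol 14.1, SAP section 2), taken here as the safety population per arm.
- p = proportion with a 7% or greater change among subjects with a post-baseline weight. Not in the documents; assumed 25%.
- m = share of safety subjects with no post-baseline weight. Not in the documents; assumed 3%, 6% and 10%.

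**Formulas.** Events = p × N × (1 − m). Divided by N, as SAP 3.8.4.1 directs, this gives p × (1 − m). Divided by N × (1 − m), the rule in SAP 3.8.4.2, it gives p.

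| m | Subjects per arm without a weight | Shown under SAP 3.8.4.1 | Shown under the SAP 3.8.4.2 rule |
|---|---|---|---|
| 3% | 135 × 0.03 = 4.05, about 4 | 25% × 0.97 = 24.25% | 25% |
| 6% | 135 × 0.06 = 8.1, about 8 | 25% × 0.94 = 23.5% | 25% |
| 10% | 135 × 0.10 = 13.5, about 14 | 25% × 0.90 = 22.5% | 25% |

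The relative reduction always equals m. If m = 0, the two denominators agree.

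**Comparison of arms, equal m.** The ratio of rates is unchanged and the difference shrinks by the factor (1 − m). With assumed rates of 30% and 20% and m = 5%, the table shows 28.5% and 19.0%, a difference of 9.5 points instead of 10.

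**Comparison of arms, unequal m.** If both arms have p = 25% but m is 3% in one and 10% in the other, the table shows 24.25% and 22.5%. The 1.75-point difference comes from the denominator alone. On 135 subjects it is 0.0175 × 135 = 2.4 subjects.

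**Scale against sampling error.** The standard error of a difference between two proportions near 25% with 135 per arm is √(2 × 0.25 × 0.75 / 135) = 0.053, or 5.3 points. The assumed artefact is about a third of that (1.75 / 5.3 = 0.33).

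**The case against.** The strongest objection is that events divided by all treated subjects is an ordinary safety incidence. The SAP summarizes adverse events by number and percentage in this same population. Subjects who left within about two weeks had little time for a 7% change from the Visit 8 baseline, and had already taken olanzapine for six weeks by then. A reader might infer from the arithmetic that the planned percentages are biased below the truth. The documents do not support that: p describes subjects who were weighed, and nothing shows that it also holds for those who were not. The figure is lower than the rate among evaluable subjects, which is a different statement.

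A reader might also infer that early dropout in general pulls the rate down, or that the treatment comparison is distorted. Neither follows. A subject who drops out early but attends the ET visit is evaluable, and no passage suggests that m is large or differs by arm. Protocol 5.3 gives all subjects two weeks of open-label samidorphan before randomization, partly so that intolerance shows itself earlier, which makes a large imbalance less likely.

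Nor is weight shown to be the only safety summary with this feature. The SAP states no evaluable-subject denominator for orthostatic changes (3.8.4.2), treatment-emergent movement disorders (3.8.6) or suicidality (3.8.7). The exception can be claimed only among the PCS tables.

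Finally, a subject weighed once at Visit 9 who then leaves remains a non-event under either denominator, and planned follow-up runs from 9 to 15 months. Changing the denominator does not deal with unequal follow-up.

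All of these limits stand. None explains why weight departs from the convention that the SAP applies to its other PCS percentages.

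**Conclusion.** The point holds as an unexplained inconsistency with a small numerical effect. Whenever m is above zero, the percentage shown is lower than the rate among subjects with a post-baseline weight, by a relative amount equal to m. At an assumed p of 25%, that is 0.75 to 2.5 points for m from 3% to 10%, with up to 1.75 points of difference between arms if m were 3% in one and 10% in the other. Both p and m are assumptions, and the visit schedule suggests that m will be small.

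The table is descriptive and no test is planned on it. By-visit weight summaries, which use observed data, are unaffected, as are the primary analysis, its significance level and its power. Weight attenuation is not among this study's objectives. This is a worthwhile tidying of the SAP and does not threaten the trial's conclusions.

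**What to change.** In SAP 3.8.4.1, replace the denominator sentence so that percentages are taken over subjects with a double-blind baseline weight and at least one post-baseline weight in the double-blind period. This matches SAP 3.8.4.2, the closest model because it too uses a change-from-baseline criterion and does not require a non-PCS baseline. Add a row showing, by arm, the number of safety-population subjects without a post-baseline weight.

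The cost is one sentence and one table row, with no new data. There is a small downside: a few randomized, dosed subjects leave the denominator, so the percentage is conditional on having been weighed after randomization. The added row offsets this, because a reader can recover the full-population figure from it and see any imbalance directly.

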3.8.4.2. Vital Signs

Descriptive statistics for vital signs and changes from baseline values at each scheduled time point will be presented as overall for the open-label periods and by treatment group for the double-blind period.

Vital sign values will be considered PCS if they meet both the observed-value criteria and the change-from-baseline criteria listed in Table 5. The number and percentage of subjects with PCS post baseline values will be tabulated by treatment group for the double-blind period. The percentages will be calculated relative to the number of subjects with available baseline values and at least 1 post baseline assessment for the double-blind period. The numerator will be the total number of subjects with available baseline values and at least 1 PCS post baseline value for double-blind period. A supportive tabular display of subjects with PCS post baseline values will be provided, including the subject ID number, study center number, and baseline and all post baseline (including non-PCS) values.

All vital signs will be presented in the subject data listing.

Orthostatic hypotension (20/10) is defined as a fall in systolic blood pressure of at least 20 mmHg and a fall in the diastolic blood pressure of at least 10 mmHg upon standing from supine. Orthostatic hypotension (30) is defined as a fall in systolic blood pressure of at least 30 mmHg upon standing from supine.

Orthostatic tachycardia is defined as a heart rate increase of 30 beats per minute (bpm) or more upon standing from supine, or over 120 bpm upon standing.

The number and percentage of subjects with orthostatic hypotension or orthostatic tachycardia occurring at any post-baseline visit will also be summarized by treatment group for the double-blind period.

Table 5: Criteria for Potentially Clinically Significant (PCS) Blood Pressure or Pulse Rate

Parameter	Criteria
Supine Systolic Blood Pressure	≤ 90 and decrease ≥ 20 mm Hg ≥ 180 and increase ≥ 20 mm Hg
Supine Diastolic Blood Pressure	≤ 50 and decrease ≥ 15 mm Hg ≥ 105 and increase ≥ 15 mm Hg
Supine Heart Rate	≤ 50 and decrease ≥ 15 bpm ≥ 120 and increase ≥ 15 bpm

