8.3.21. Vital Signs

Vital signs (ie, blood pressure, pulse, respiratory rate, and oral body temperature) will be assessed at the time points specified in [Table 1](#), [Table 2](#), and [Table 3](#).

An effort will be made to consistently use the same arm (preferably the subject’s dominant arm) to measure blood pressure and pulse throughout the study. The blood pressure cuff will be calibrated per study site standard operating procedure. Automated measurement is preferred, but if performed manually, pulse will be measured in the brachial artery for at least 30 seconds.

Orthostatic blood pressure, pulse, and respiration rate will be collected each time vital signs are measured (except at screening) in the following manner:

- Allow subject to be in a supine position for at least 5 minutes
- Measure blood pressure, pulse, and respiration rate
- Have subject stand for 2 minutes
- Measure blood pressure, pulse, and respiration rate

Vital signs may be collected at any time during a visit where it is scheduled.

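### Two patterns of postural blood-pressure fall are left out of the by-arm orthostatic hypotension count in SAP 3.8.4.2

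*SAP*

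**What the plan says.** Protocol 8.3.21 provides the data: "Orthostatic blood pressure, pulse, and respiration rate will be collected each time vital signs are measured", except at screening, with the subject first supine and then standing for 2 minutes.

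SAP 3.8.4.2 gives two definitions of orthostatic hypotension:

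- (20/10): "Orthostatic hypotension (20/10) is defined as a fall in systolic blood pressure of at least 20 mmHg and a fall in the diastolic", continuing "blood pressure of at least 10 mmHg upon standing from supine".
- (30): "Orthostatic hypotension (30) is defined as a fall in systolic blood pressure of at least 30 mmHg upon standing from supine", with no diastolic condition.

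The by-arm count for the double-blind period is then specified: "The number and percentage of subjects with orthostatic hypotension or orthostatic tachycardia occurring at any post-baseline visit will also be summarized by treatment group". The unit is the subject, at any post-baseline visit.

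The same section also plans other displays of vital signs. These are descriptive summaries ("Descriptive statistics for vital signs and changes from baseline values at each scheduled time point will be presented"), a full listing ("All vital signs will be presented in the subject data listing"), and Table 5, whose blood-pressure criteria are supine (for example "Supine Systolic Blood Pressure"). It does not say whether supine-to-standing differences are among the descriptive summaries.

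**The concern.** Safety and tolerability is the only secondary objective (Protocol 6.2, SAP 1.1). The orthostatic table is the one planned by-arm count built on the paired supine and standing pressures. The first definition needs both components. The second relaxes this only for systolic falls of 30 mmHg or more, and nothing relaxes it for diastolic falls. A subject whose diastolic pressure drops substantially, but whose systolic pressure drops by less than 20 mmHg, is therefore never counted, however large the diastolic drop.

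At stake is how completely postural falls are described by arm. The primary endpoint, power and type I error are not involved.

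**Working it through.** **Step 1: which patterns are counted.** Each pair below is systolic fall/diastolic fall in mmHg.

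| Pair | (20/10) | (30) | Counted |
|---|---|---|---|
| 20/10 | yes | no | yes |
| 30/0 | no | yes | yes |
| 35/5 | no | yes | yes |
| 20/9 | no | no | no |
| 25/5 | no | no | no |
| 29/9 | no | no | no |
| 15/12 | no | no | no |
| 0/15 | no | no | no |

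The uncounted either-component falls are therefore of two kinds: systolic 20 to 29 with diastolic under 10, and diastolic 10 or more with systolic under 20.

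**Step 2: how many could be missed.** The plan states no figure to reproduce and gives no mean, SD or correlation for postural change. Everything from here rests on assumed inputs.

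Let S and D be the systolic and diastolic falls, taken as bivariate normal. Per reading:

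- either = P(S≥20) + P(D≥10) − P(S≥20 and D≥10)
- counted = P(S≥20 and D≥10) + P(S≥30) − P(S≥30 and D≥10)

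The SAP counts subjects over visits. Protocol Table 2 schedules vital signs at Visits 9, 10, 12, 14, 16, 18, 20, 22, 24 and 26, which is 10 post-baseline visits in the 9-month period. If visits are independent, the subject-level probability is 1 − (1 − p)^10, and the missed share is 1 − counted/either at subject level.

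*Case A, small falls.* Mean fall 2 systolic and −2 diastolic (a slight rise), SDs 9 and 6, correlation 0.5.
- Standardised thresholds: (20−2)/9 = 2; (10+2)/6 = 2; (30−2)/9 = 3.11.
- either = 0.02275 + 0.02275 − 0.00405 = 0.04145.
- counted = 0.00405 + 0.00093 − 0.00034 ≈ 0.00465 (from unrounded terms).
- Over 10 visits: either 0.345, counted 0.0455. Missed = 1 − 0.0455/0.345 ≈ 0.87.

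*Case B, larger and tightly correlated falls.* Mean fall 10 and 5, SDs 20 and 10, correlation 0.9.
- Standardised thresholds: 0.5, 0.5 and 1.
- either = 0.30854 + 0.30854 − 0.24533 = 0.37175.
- counted = 0.24533 + 0.15866 − 0.14967 = 0.25432.
- Over 10 visits: either 0.990, counted 0.947. Missed = 1 − 0.947/0.990 ≈ 0.044, near the 5% end.

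**Step 3: allowing for correlation between visits.** Four simulated scenarios used 11 visits, with 40% of the variance between subjects.

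| Mean fall S/D | SD S/D | Correlation | Either | Missed |
|---|---|---|---|---|
| 0/−5 | 12/7 | 0.5 | 34% | 77% |
| 0/0 | 12/7 | 0.5 | 51% | 73% |
| 5/0 | 12/7 | 0.5 | 62% | 60% |
| 10/3 | 15/10 | 0.7 | 87% | 26% |

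Per reading, the missed share was 51% to 99% over a grid of 243 scenarios. It was 31% to 46% in five further scenarios with larger mean falls, wider systolic spread or higher correlation. Per-reading shares do not describe the SAP table, because a subject missed at one visit can be counted at another. Case B shows the gap: 1 − 0.25432/0.37175 = 32% per reading, but about 4% per subject.

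**The case against.** The two SAP rules can be read as a deliberate two-tier scheme: a moderate systolic fall must be corroborated by the diastolic, while a large one stands alone. Nothing in either document requires an either-component rule, and no passage contradicts the SAP. That stands, so the point is a request for fuller reporting and does not allege an error.

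An either-component count over many visits is also less specific. Taking 4.2% to 18.1% of readings as an assumed rate, 10 independent visits give 1 − 0.958^10 = 35% to 1 − 0.819^10 = 86% of subjects. Such a row could blur a contrast between arms, so it should sit beside the present counts and not replace them.

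Four stronger readings are tempting, and the documents do not support them:

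- *Orthostatic hypotension is counted only when both pressures fall.* The (30) rule contradicts this.
- *These falls appear in no safety output.* All vital signs are listed, and standing values are not excluded from the descriptive summaries. A fall with a qualifying heart-rate response enters the orthostatic tachycardia count, and a clinically significant one may be recorded as an adverse event (Protocol 13.1). These routes are incidental, however, and none gives a by-arm incidence of the two patterns.
- *The measures are taken at every visit.* Screening has no orthostatic measures (Protocol 8.3.21), and dispensing-only visits have no clinical assessments (Protocol Section 8).
- *A difference between arms is being hidden.* No calculation shows this. The same rule applies to both arms, and both take olanzapine.

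**Conclusion.** The gap is real and follows from the definitions alone: the two patterns in Step 1 do not enter the by-arm orthostatic hypotension count, and Table 5 cannot catch them.

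Its size is unknown. Under assumed bivariate normal changes and about 10 assessed visits, the missed share of subjects with an either-component fall runs from about 5% to 87%. Those ends are illustrations and not bounds; they move with the assumed means, spreads, correlation and number of visits. A reader might infer that most such subjects are lost, or that reported incidence is far too low. Some inputs give that result and others do not, and the documents offer no way to choose between them.

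This is a minor improvement to safety reporting. The primary analysis is unaffected.

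**What to change.** In the orthostatic hypotension table of SAP 3.8.4.2, add a row for subjects with a systolic fall of at least 20 mmHg or a diastolic fall of at least 10 mmHg on standing, at any post-baseline visit with vital signs. Under it, show systolic-only, diastolic-only and both, where both is the present (20/10) rule. Keep the (30) row as it is.

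The data are already collected and both existing counts stay visible. The cost is a sentence in the SAP and a few table rows. The downside is a higher, less specific headline percentage in both arms, which the sub-rows let a reader interpret.
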